2. BASELINE DOCUMENTATION OF TARGET AND NON-TARGET LESIONS

2.1. TARGET LESIONS

All measurable lesions up to a maximum of five lesions total (and a maximum of two lesions per organ) representative of all involved organs should be identified as Target lesions and will be recorded and measured at baseline.

Target lesions should be selected on the basis of their size (lesions with the longest diameter), be representative of all involved organs, but in addition should be those that lend themselves to reproducible repeated measurements.

A Total Measured Tumor Burden (TMTB) for all target lesions will be calculated and reported as the baseline TMTB. The TMTB results from adding:

- the longest diameters of all non-nodal target lesions, and
- the short axis for all nodal lesions

The baseline TMTB will be used as reference to further characterize any objective tumor regression/progression in the measurable dimension of the disease.

2.2. NON-TARGET LESIONS

All other lesions (or sites of disease) not selected as Target lesions should be identified as Non-Target lesions and should also be recorded at baseline. There is no limit to the number of Non-Target lesions that can be recorded at baseline. In addition, it is possible to record multiple non-target lesions involving the same organ as a single item on the CRF (e.g. “multiple enlarged pelvic lymph nodes” or “multiple liver metastases”).

Measurements are not required and these lesions should be followed as “present”, “absent”, or in rare cases “unequivocal progression”.

Baseline selected Non-target lesions can never convert to measurable lesions, not even if they increase in size at subsequent timepoints and become “measurable”. Only true New lesions can be measured and can contribute to the TMTB if measurable.

3. METHODS OF ASSESSMENT

The same method of assessment and the same technique used at baseline to characterize each lesion must be used at each subsequent post-baseline assessment. All measurements should be recorded in metric notation, using calipers if clinically assessed.

3.1. CT AND MRI

CT is the best currently available and reproducible method to measure lesions selected for response assessment. In the TRIO026 study it is recommended that CT examinations of the chest, abdomen, and pelvis will be used to assess tumor burden at baseline and follow-up visits. CT examination with intravenous (i.v.) contrast media administration is the preferred method. Measurability threshold of lesions on CT scan is based on the assumption that CT slice thickness is 5mm or less. When CT scans have slice thickness greater than 5 mm, the minimum size for a measurable lesion should be twice the slice thickness.

MRI should be used where CT is not feasible or it is medically contra-indicated. MRI has excellent contrast, spatial and temporal resolution; however, there are many image acquisition variables involved in MRI, which greatly impact image quality and lesion measurement. For these reasons, CT is the imaging modality of choice.

3.2. CLINICAL LESIONS

In TRIO026, clinical examination will not be used for assessment of TL. Clinically detected lesions can be selected as target lesions only in case they are assessed by CT or MRI scans. In this case, measurement will be based on the CT/MRI and not on clinical examination. Clinical examination can be used to assess NTL and to identify the presence of new lesions.

3.3. CHEST X-RAY

In TRIO026, chest x-ray will not be used for assessment of TL/NTL as they will be assessed by CT/MRI.

3.4. ULTRASOUND

In TRIO026, ultrasound will not be used for assessment of TL/NTL as it is not a reproducible method, does not provide an accurate assessment of tumor size and is operator dependent. Ultrasound examination can be used to identify the presence of new lesions if new lesions are identified by ultrasound in the course of the study, confirmation by CT or MRI is advised.

3.5. ENDOSCOPY AND LAPAROSCOPY

The utilization of these techniques for objective tumor evaluation is not advised.

3.6. CYTOLOGY AND HISTOLOGY

In TRIO026 histology will not be used as part of the tumor response assessment as per irRECIST.

Cytological confirmation of the neoplastic origin of any effusion that appears or worsens during treatment is required when the measurable disease has met criteria for response or stable disease. In such circumstances, the cytology is necessary to differentiate between response / stable disease (an effusion may be a side effect of the treatment) and progressive disease (if the neoplastic origin of the fluid is confirmed). Where cytology findings are not available, any effusion that significantly worsens (from trace to large) or appearance of clinically significant effusion (requiring change in drug therapy) during the study treatment will be considered to be progression of NTL, or disease progression due to new lesions.

3.7. BONE SCAN

Bone lesions identified on a bone scan at baseline and confirmed as tumor lesions by CT/MRI at baseline should be recorded as NTL and followed by the same method as per baseline assessment.

In TRIO026 bone scans may be used as a method of assessment to identify the presence of new bone lesions at follow-up visits. New lesions will be recorded where a positive hot-spot that was not present on the baseline bone scan assessment (if available) is identified on a bone scan performed at any time during the study. Confirmation by CT, MRI and x-ray is recommended where bone scan findings are equivocal.

3.8. FDG-PET SCAN AND PET-CT

In TRIO026, PET scans may be used as a method for identifying new lesions, according with the following algorithm:

- New lesions will be recorded where there is positive FDG uptake not present on baseline FDG-PET scan (if available) or in a location corresponding to a new lesion on CT/MRI at the same follow-up visit.
- If there is no baseline FDG-PET scan available, and no evidence of new lesions on CT/MRI scans then follow-up CT/MRI assessments should be continued, scheduled as per protocol or clinical indicated, in order to confirm new lesions in subsequent tumor assessments

Low dose or attenuation correction CT portions of a combined PET–CT are of limited use in efficacy assessments in clinical trials and therefore they should not substitute dedicated diagnostic contrast enhanced CT scans. In exceptional situations, if a site can document that the CT performed as part of a PET–CT is of identical diagnostic quality to a diagnostic CT (with IV and oral contrast) then the CT portion of the PET–CT can be used for irRECIST measurements. However, this is not recommended because the PET portion of the CT introduces additional data that may bias an Investigator if it is not routinely or serially performed.

4. POST-BASELINE: TMTB

At each post-baseline assessment the TMTB is defined as the sum of:

- Longest diameters of all non-nodal target lesions
- Longest diameters of all NEW non-nodal measurable lesions
- Short axis of all nodal target lesions
- Short axis of all NEW nodal measurable lesions

Definition of New Measurable Lesion

In order to be selected as new measurable lesions (≤ 2 lesions per organ, ≤ 5 lesions total, per timepoint), new lesions must meet criteria as defined for baseline target lesion selection and meet the same minimum size requirements of 10 mm in long diameter and minimum 15 mm in short axis for new measurable lymph nodes. New measurable lesions shall be prioritized according to size, and the largest lesions shall be selected as new measured lesions.

5. POST-BASELINE: NON-TARGET LESIONS ASSESSMENT

Non-Target lesions assessment

The RECIST 1.1 definitions for the assessment of non-target lesions apply:

- Complete Response (CR): Disappearance of all non-target lesions. All lymph nodes must be non-pathological in size (< 10mm short axis).
- Non-CR/Non-PD (irNN): Persistence of one or more non-target lesion(s).
- Progressive Disease (PD): Unequivocal progression of existing non-target lesions (note: the appearance of unequivocal new lesions is also considered progression).

The response of non-target lesions primarily contributes to the overall response assessments of irCR and irNon-CR/Non-PD (irNN). Non-target lesions do not affect irPR and irSD assessments. Only a massive and unequivocal worsening of non-target lesions alone, even without progress in the TMTB is indicative of irPD.

Definition of New Non-Measurable lesions

All new lesions not selected as New Measurable lesions are considered New Non-measurable lesions and are followed qualitatively. Only a massive and unequivocal progression of New Non-measurable lesions leads to an overall assessment or irPD for the given timepoint. Persisting new Non-measurable lesions prevent irCR.

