6. IMMUNE-RELATED OVERALL TUMOR ASSESSMENT AT EACH TIMEPOINT

Immune-related Complete Response (irCR): complete disappearance of all measurable and non-measurable lesions. Lymph nodes must decrease to < 10 mm in short axis.

Immune-related Partial Response (irPR): decrease of $\geq 30\%$ in TMTB relative to baseline, non-target lesions are irNN, and no unequivocal progression of new non-measurable lesions.

Immune-related Stable Disease (irSD): failure to meet criteria for irCR or irPR in the absence of irPD.

irNN: no target disease was identified at baseline and at follow-up the patient fails to meet criteria for irCR or irPD.

Immune-related Progressive Disease (irPD): minimum 20% increase and minimum 5 mm absolute increase in TMTB compared to nadir, or irPD for non-target or new non-measurable lesions.

irNE (Not evaluable): used in exceptional cases where insufficient data exists.

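### Appendix 2 section 5 keeps a RECIST 1.1 note on new lesions that contradicts the irRECIST rule for new measurable lesions and is overridden only by implication

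*Protocol*

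**What the plan says.** All of the text is in Protocol Appendix 2 (irRECIST).

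- Section 5 adopts the RECIST 1.1 categories for non-target lesions. Its definition of progression for that category ends with a parenthesis, "note: the appearance of unequivocal new lesions is also considered progression", which sets no limit on lesion type or size.
- Section 5 then says that non-target lesions have no bearing on irPR or irSD, and adds two restrictions. For non-target lesions: "Only a massive and unequivocal worsening of non-target lesions alone, even without progress in the TMTB is indicative of irPD". For new non-measurable lesions: "Only a massive and unequivocal progression of New Non-measurable lesions leads to an overall assessment or irPD for the given timepoint".
- Section 2.2 says of new lesions: "Only true New lesions can be measured and can contribute to the TMTB if measurable". Section 4 puts them into the post-baseline TMTB ("Longest diameters of all NEW non-nodal measurable lesions", and likewise the short axis of new nodes), subject to the "same minimum size requirements of 10 mm in long diameter and minimum 15 mm in short axis for new measurable lymph nodes".
- Section 6 defines overall irPD as "minimum 20% increase and minimum 5 mm absolute increase in TMTB compared to nadir, or irPD for non-target or new non-measurable lesions". Its irPR definition requires "no unequivocal progression of new non-measurable lesions", so it presupposes that a responder may have new lesions.
- Section 8 makes new measurable lesions irPD on appearance for patients who had no target lesions at baseline.

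SAP section 3.4.1 takes best overall response as the investigator assessed it. It adds no rule of its own for new lesions.

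**The concern.** Section 6 accepts irPD of the non-target category as sufficient for overall irPD, and the note sits inside that category's definition of progression. An investigator who follows the note literally could therefore call irPD for any clear new lesion. One who follows sections 2.2, 4 and 6 would add the lesion to TMTB and might call irSD or irPR.

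The call matters in three places. It dates the Part B primary endpoint, irPFS. It feeds Part A best overall response and the futility rule in Protocol section 3.3. It also obliges the site to stop study treatment under Protocol section 5.5. Part B is open-label and investigator-assessed, with approximately 25 sites in two countries, so a uniform reading depends on the wording of this appendix.

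**Working it through.** **1. Which lesions are affected.**

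| New finding | Under the note | Under the irRECIST rules |
|---|---|---|
| New non-measurable lesion | progression | irPD only if massive and unequivocal (express limit, section 5) |
| New measurable lesion, TMTB at or above the threshold | progression | irPD (section 6) |
| New measurable lesion, TMTB below the threshold | progression | irSD or irPR (sections 4 and 6; no express limit on the note) |
| New measurable lesion, no target lesions at baseline | progression | irPD (section 8) |

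The third row is the case with a conflict and no sentence that expressly settles it.

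**2. When a lesion falls in that row.** Let s be the summed size of the new measurable lesions, with targets unchanged at nadir N. The rise is s/N. Every s is at least 10 mm, so the 5 mm condition is always met and only the 20% condition matters. The readings diverge when s/N < 0.20, that is, N > s/0.20.

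- One 10 mm non-nodal lesion: 10/0.20 = 50 mm.
- One 15 mm node: 15/0.20 = 75 mm.
- Two 10 mm lesions: 20/0.20 = 100 mm.
- Five 10 mm lesions (the section 4 maximum per time point): 50/0.20 = 250 mm.

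A 50 mm nadir corresponds to a mean target size of 50/2 = 25 mm with two targets, 50/3 = 16.7 mm with three, or 50/5 = 10 mm with five. Five is the maximum number of targets, and 10 mm is the smallest measurable non-nodal size.

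**3. Hypothetical examples.**

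- Nadir 100 mm, targets unchanged, one new 12 mm lesion: 112/100 − 1 = +12%. This is irSD by TMTB and progression by the note.
- First post-baseline scan, baseline 100 mm, targets now 55 mm, one new 10 mm lesion: (55 + 10)/100 − 1 = −35%. This is irPR by TMTB, provided non-target lesions are irNN and no new non-measurable lesion has progressed. It is progression by the note.
- Boundary: nadir 50 mm plus a new 10 mm lesion is +20%, and both readings give irPD.

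**4. Do the safeguards settle it?** Section 7 requires confirmation of irPD in the first 12 weeks of treatment (84 days) and only recommends it later.

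- Part A: the 6-week scan is inside the window. The next scheduled scan, at 6 + 12 = 18 weeks, is outside.
- Part B: the first scan is 84 ± 7 days from randomization, and treatment starts 0 to 3 days after randomization. The scan therefore falls between treatment day 77 − 3 = 74 and day 91, on either side of the limit.

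Confirmation does not resolve the conflict in any case. A repeat scan of a small persisting lesion confirms progression under the note and leaves irSD under TMTB. The section 8 advice to continue and reassess is for doubtful progression, not for a clear lesion.

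**5. Scale in Part A.** One reclassified subject moves a cohort's irDCR or irORR by 1/n: 1/5 = 20.0 points at five subjects, 1/8 = 12.5 points at eight. The analysis is by ITT, so n can exceed five. A cohort becomes futile only if every subject otherwise counted as irCR, irPR or irSD is reclassified. These figures show what one misread would do. They do not estimate how often it happens.

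**The case against.** The strongest reply is that the appendix already answers the question. The note belongs to a sub-category, and section 5 at once says that this sub-category does not affect irPR or irSD. The first restriction in section 5 limits the only limb of the section 6 definition that the note could use. Section 6 does not list new measurable lesions as a separate trigger, because section 4 has put them into TMTB. The section 8 rule for patients without target lesions would be redundant if the note applied to everyone. The introduction to the appendix gives regression despite new lesions as a reason for using irRECIST.

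Most of this stands. A reader might infer that nothing overrides the note, or that the plan has no rule for new measurable lesions. The documents do not support that: read together, sections 4, 5, 6 and 8 supply the rule, and it is the TMTB rule.

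What remains is that the override has to be worked out. Under section 2.2 non-target lesions are recorded at baseline, so the first restriction does not literally address a new measurable lesion. If it barred every other irPD without TMTB progress, it would contradict the paragraph that follows, which allows irPD from new non-measurable lesions. The second restriction covers non-measurable lesions only. Some other text leans the literal way: section 3.6 speaks of progression through new lesions when an effusion appears or worsens, and section 8 names a new lesion as a source of doubtful progression.

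**Conclusion.** The concern holds as a minor inconsistency in the endpoint criteria. The note contradicts sections 2.2, 4 and 6, and it is overridden by implication but never expressly. A clear new measurable lesion below the TMTB threshold can therefore be read as irPD or as irSD/irPR. An example is one 10 mm lesion with unchanged targets and a nadir above 50 mm. Followed literally, the note gives the wrong call.

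A reader might go further and infer that irPFS is biased, that power or type I error is affected, or that a Part A cohort could be wrongly rejected as futile. The documents do not support any of these as a finding. They give no frequency of such lesions and no sign that any site has used the note, so the effect on irPFS, irORR or irDCR cannot be quantified. The thresholds above rest on the size limits in the appendix and on targets unchanged at nadir; the examples are hypothetical.

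**What to change.** In Appendix 2 section 5, delete the parenthesis. Add one sentence: new lesions lead to irPD only through TMTB if measurable, or through massive and unequivocal progression if non-measurable. Name two exceptions in that sentence, so that it does not create a new conflict: subjects with no target lesions at baseline (section 8), and the rule in section 3.6 for effusions that appear or worsen.

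Send the same clarification to the sites. As a precaution, check before the Part A futility review whether any irPD was called on new lesions alone.

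The cost is one deletion, one sentence, a note to sites and a recheck of existing Part A reads. No extra scans or patients are needed. Protocol section 3.2 already allows for an amendment before Part B, which could carry the change.

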6. IMMUNE-RELATED OVERALL TUMOR ASSESSMENT AT EACH TIMEPOINT

Immune-related Complete Response (irCR): complete disappearance of all measurable and non-measurable lesions. Lymph nodes must decrease to < 10 mm in short axis.

Immune-related Partial Response (irPR): decrease of $\geq 30\%$ in TMTB relative to baseline, non-target lesions are irNN, and no unequivocal progression of new non-measurable lesions.

Immune-related Stable Disease (irSD): failure to meet criteria for irCR or irPR in the absence of irPD.

irNN: no target disease was identified at baseline and at follow-up the patient fails to meet criteria for irCR or irPD.

Immune-related Progressive Disease (irPD): minimum 20% increase and minimum 5 mm absolute increase in TMTB compared to nadir, or irPD for non-target or new non-measurable lesions.

irNE (Not evaluable): used in exceptional cases where insufficient data exists.

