3.3 Part A: Determination of the Optimal Schedule for Part B

The optimal schedule to be used in Part B will be selected after analysis of the accumulated safety and efficacy data from Part A by the Steering Committee. The analyses will be conducted once 5 subjects in each cohort are considered evaluable. Subjects will be considered evaluable once they have:

- Completed at least two CC-486 cycles
- Undergone the 1st post-baseline tumor burden assessment
- Undergone the 2nd tumor biopsy and adequate paired tissue obtained

Full details of the criteria to be used to guide the Steering Committee in their selection of the optimal regimen will be described in the Steering Committee Charter. In general, however, the following decision criteria will be applied:

- Step 1: Safety and Futility evaluation:

A cohort will be rejected due to toxicity if any of the below criteria is met:

- One grade 5 AE related to study drugs
- More than one subject experiencing a grade 4 AE related to study drugs (other than hypothyroidism)

- More than 2 subjects experiencing a grade 3 AE related to study drugs (other than hypothyroidism)

A cohort will be rejected due to futility if at least one response or stable disease (irPR, irCR or irSD) is not observed in that schedule.

- Step 2: Determination of the optimal schedule: In the cohort(s) not rejected due to toxicity or due to futility, the selection by the Steering Committee of the optimal schedule will be based on the toxicity profile and the irORR of each cohort (irDCR may also be considered for the determination of the optimal schedule). For example, if one cohort has higher irORR and similar toxicity profile compared to another cohort, the first one will be selected as optimal. If two or more cohorts have the same irORR, the optimal schedule will be established based primarily on the more favorable toxicity profile. Additionally, data from the correlative analyses to be done in the biologic samples described in section 6.4.7, may be taken into consideration for determining the optimal schedule.

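### Appendix 2 contradicts itself on irPR: section 6 requires a non-target lesion to persist, section 5 says non-target lesions do not matter, so the same scans can be scored irPR or irSD

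*Protocol*

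**What the plan says.** Protocol Appendix 2 gives the response rules that investigators apply in both parts.

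- **Section 5** sorts non-target lesions into three states. Complete response is "Disappearance of all non-target lesions", with nodes back to non-pathological size. irNN is "Persistence of one or more non-target lesion(s". The third state is progression. The same section then states: "Non-target lesions do not affect irPR and irSD assessments".
- **Section 6** assigns the overall response at each timepoint. irPR needs a decrease of at least 30% "in TMTB relative to baseline, non-target lesions are irNN, and no unequivocal progression of new non-measurable lesions". irSD is the default category: "failure to meet criteria for irCR or irPR in the absence of irPD".
- **Section 6** also uses irNN in a second sense, as an overall response: "irNN: no target disease was identified at baseline and at follow-up the patient fails to meet criteria for irCR or irPD".

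irORR is the proportion with a best overall response of irCR or irPR by investigator assessment (SAP 3.4.1; protocol synopsis, Statistical Methods). In Part A it guides Step 2 of the schedule choice. The example in Protocol 3.3 reads: "if one cohort has higher irORR and similar toxicity profile compared to another cohort, the first one will be selected as optimal". In Part B irORR is a secondary endpoint, and irDoR starts when irPR or irCR is first met.

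**The concern.** The two sections give different answers for the same patient. If section 6 is followed to the letter, losing all non-target disease is scored lower than keeping some of it, which no response criterion should do.

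Nothing later in the plan resolves the conflict. Protocol 8.4 and 8.5 and SAP 3.4.1 rely on the investigator's assessment, and no central read of response is described. Appendix 2, section 7, asks for no confirmation of response, so a single timepoint can set the best overall response. The SAP has no algorithm that derives timepoint response from the lesion data.

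The Part A irORR feeds the decision that fixes the experimental arm of Part B. Part B is open-label, so inconsistent scoring there need not be balanced between arms.

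**Working it through.** **Step 1: compare the rules.** Take a subject with TMTB down at least 30%, some target disease remaining and no progression of new lesions.

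| Non-target status | Section 6, read literally | Section 5 sentence |
|---|---|---|
| At least one lesion persists (irNN) | irPR | irPR |
| All lesions gone (non-target CR) | not irPR, not irCR, not irPD, so irSD | irPR |
| None at baseline | irSD if the condition counts as failed; irPR if it counts as not applicable | irPR |
| Unequivocal progression | irPD | irPD |

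The second row is a direct contradiction and the third is an ambiguity. The second meaning of irNN does not help, because it covers only subjects without target disease at baseline.

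**Step 2: who would lose a response.** Best overall response is used and no confirmation is needed. A subject therefore drops out of irORR only if she never has a timepoint with at least 30% shrinkage while a non-target lesion persists, and never reaches irCR. A subject who clears non-target disease after an earlier irPR keeps that irPR. A subject first scored irSD who later reaches irCR stays a responder, but her irDoR starts later.

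**Step 3: which endpoints move.**
- irORR and irDoR can move.
- irDCR counts irCR, irPR and irSD together, so moving a subject from irPR to irSD leaves it unchanged.
- The Part A futility rule (Protocol 3.3, Step 1) also accepts irSD, so it is unchanged.
- irPD is judged against the TMTB nadir and on unequivocal lesion progression, not on whether irPR was reached. irPFS, its event count and the Part B sample size are unaffected.

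**Step 4: size in Part A.** One reclassified subject moves a cohort's irORR by 1/n. With n = 5, 1/5 = 20 percentage points. The SAP computes irORR on the ITT population, which keeps enrolled subjects who were replaced as non-evaluable, so n may be larger: 1/6 = 16.7 points, 1/7 = 14.3 points.

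**Step 5: illustration for Part B.** Let s be the share of responders reclassified to irSD. The documents give no figure for s, so the values below are assumptions. Observed irORR = true irORR × (1 − s), and responders lost per arm = 75 × irORR × s. The 11.5% is the pembrolizumab response rate in Protocol 1.4.1; the 20% is assumed. All responses are taken to be irPR, and all sites are taken to apply section 6 literally.

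| s | From 11.5% | Lost of 75 | From 20% | Lost of 75 |
|---|---|---|---|---|
| 0 (section 5 applied) | 11.5% | 0 | 20% | 0 |
| 10% | 10.4% | 0.9 | 18% | 1.5 |
| 25% | 8.6% | 2.2 | 15% | 3.75 |
| 50% | 5.8% | 4.3 | 10% | 7.5 |

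If s is the same in both arms, the ratio of response rates is unchanged, since (1 − s) cancels, and the difference shrinks by the factor (1 − s).

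**The case against.** A reader might infer that Appendix 2 scores these subjects irSD, so that irORR is undercounted in both parts. The documents do not support that. Section 5 says the opposite in plain terms, and a site that follows it loses no responder. What is established is a conflict between two rules, not a bias in one direction.

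Other points for the plan also carry weight:

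- **No baseline non-target disease.** A condition on lesions that do not exist is easily read as not applicable. Section 8 of the appendix, on subjects without target lesions, states irPR as a TMTB decrease alone, which fits section 5. This case is only ambiguous.
- **Few subjects.** Expected reclassifications per cohort of 5 are small even under the literal reading: 5 × 0.115 × 0.10 = 0.06 with a 10% share, or 5 × 0.20 × 0.30 = 0.3 with a 20% response rate and a 30% share (rate and shares assumed, apart from the 11.5%).
- **Step 2 is a judgement.** The Steering Committee also weighs toxicity and may use irDCR and correlative data, under a charter that is not among the documents.
- **The data would show it.** The tumor assessment listing in SAP 5.2 gives lesion measurements and timepoint response for each patient.

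These points limit the size of the problem. They do not remove it: section 6 is where the overall response is assigned, an investigator would naturally turn to it, and its wording gives a perverse result for cleared non-target disease.

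**Conclusion.** Wrong as written (internal contradiction). Sections 5 and 6 of Appendix 2 cannot both be applied to a subject with at least 30% shrinkage, residual target disease and cleared non-target lesions. Neither the protocol nor the SAP says which governs.

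The effect on irORR ranges from zero, if section 5 is applied, to an unknown downward bias, if section 6 is applied literally. In Part A the most that one subject can do is move a cohort by 20 percentage points, and less if the ITT cohort exceeds 5. That could matter where two schedules have similar toxicity. The Part B figures are illustrations that rest on an assumed share, not estimates.

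The finding on the text is firm; the size is not known. It is worth correcting because irORR informs the schedule choice and the correction is cheap. It gives no reason to doubt the Part B primary analysis.

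**What to change.** In Appendix 2, section 6, replace the irPR condition that non-target lesions be irNN with one that accepts non-target CR, irNN, or no non-target lesions at baseline, that is, no unequivocal non-target progression. This brings section 6 into line with section 5. Giving the two uses of irNN separate names in the same edit would remove the remaining ambiguity.

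For Part A, use the planned tumor assessment listing to find any timepoint with a TMTB decrease of at least 30% that was scored irSD, and query the site. A query keeps the endpoint investigator-assessed and does not presume that an error was made.

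The cost is one line in the appendix, a matching line in the CRF completion guidelines and a short listing check. No new data are needed, since lesion measurements and responses are already to be listed.
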